2. OBJECTIVES

The primary objective of study A is:

• To evaluate the use of real-time visual and audio feedback on the knee adduction moment during gait in patients with knee osteoarthritis to decrease the biomechanical load on the knee via implicit learning and explicit instructions.

The secondary objective of study A is:

- To evaluate changes in the kinematic patterns and electromyographic patterns between baseline (without feedback) and modified (with feedback) gait patterns.
- To identify factors based on the demographic, radiographic and baseline kinematics which increase the likelihood in reducing the KAM using the biofeedback training method.

The primary objectives of study B are:

- To provide proof-of-concept for the use of real-time feedback as a clinical intervention on gait retraining to decrease the biomechanical load on the knee in patients with knee osteoarthritis during a 6 weeks training and 3 and 6 months follow-up.
- To assess changes in pain and function as a result of the biofeedback gait training programme; this will be measured using the WOMAC questionnaire and NRS pain scale. Pain and function are important outcome measures for the patient and are therefore included as additional primary outcome measures.

The secondary objective of study B is:

i) To estimate the reduction in cognitive demand (and hence the extent of motor learning) of the gait modifications over the six week retraining period.

3. STUDY DESIGN

Cross-sectional observational study (A) and an uncontrolled experimental study (B).

Study A: A biofeedback algorithm using computer modeling will be tested on its feasibility in a cross-sectional observational study to establish measurement capability and quality in patients with KOA (n=41).

Study B: Secondly, an uncontrolled experimental study will be carried out to provide preliminary evidence for real-time feedback as an intervention in modifying gait in a subsample of the previous study (n=30). Participants will begin with weekly training sessions for a period of six weeks. Follow up measurements will be conducted during the final training

Version number: 5, 18-05-16

week and at 3 and 6 months after completion of the training to assess long term effects in both groups; hence for each group there will be a total of 4 full assessments (week 1 and 6 of the training sessions and 3 and 6 month follow ups) for study B in addition to the initial measurement for study A. Note, a full assessment will include measurement of kinematics and kinetics (specifically KAM) plus questionnaire based data; WOMAC pain and function. and knee confidence. At the interim training weeks, pain will be assessed using the Numeric Rating Scale (NRS) pain scale. Further details of the timing of assessments at each stage of Study B is presented in Appendix A2

| | Week number | | | | | | | | | | | | | |
|--------------------------|-----------------------|----|----|----|----|----|--|---|---|----|----|----|----|----|
| 30 patients from Study A | 1 | 2 | 3 | 4 | 5 | 6 | 7 | 8 | 9 | 10 | 11 | 12 | 18 | 30 |
| | start of intervention | | | | | M2 | Home practice of modified gait pattern | | | | M3 | M4 | | |
| | M1 | T2 | Т3 | T4 | T5 | T6 | | | | | | | | |
| | T1 | | | | | | | | | | | | | |
| | | | | | | | | | | | | | | |
| | | | | | | | | | | | | | | |
| | | | | | | | | | | | | | | |

T1 to T6 indicate training sessions 1 to 6. M1 to M4 indicate measurement sessions 1 to 4. Further details relating to the measurements at each stage of the protocol can be found in Appendix A2.

| and audio feedback, depending on the results of oes (ensure flat shoes and same/ similar shoes worn |
|--|
| sults of study A, thout feedback while new pattern is applied thout feedback while new pattern is applied and s applied * training (e.g. gait pattern, stair climbing, getting-up ng) be a week during 6 weeks week 44 to 6 ment after 3 and 6 months: blication of the learned pattern |
| |
| |

4. STUDY POPULATION

4.1 Population (base)

In the present study, patients from the Amsterdam Osteoarthritis (AMS-OA) cohort with a unilateral or bilateral diagnosis of knee OA according to the American College of Rheumatology (ACR) will be included [73-75]. The AMS-OA cohort contains patients with OA of the knee and/or hip who have been referred to a secondary care outpatient rehabilitation center (Reade, Center for Rehabilitation and Rheumatology, Amsterdam, the Netherlands). The examination protocol involves assessments by rheumatologists, radiologists and rehabilitation physicians. Further patients will be recruited directly through the VUmc and will be assessed by a VUmc rheumatologist. These patients will therefore not form part of the AMS-OA cohort but will require a radiograph of the knees to determine if they meet the inclusion criteria. All patients will provide informed consent according to the Declaration of Helsinki. The study will be submitted for approval to the Institutional Review Board of the VUmc. 30 patients from study A will also be enrolled in study B. Where there are > 30 patients meeting the criteria for study B (as specified in section 4.2), patients will be selected at random from the total number of potential study subjects.

4.2 Inclusion criteria

Inclusion criteria for the present study (A and B) are knee osteoarthritis on the medial compartment based on the ACR criteria (ACR criteria are age over 50 years, morning stiffness less than 30 minutes, crepitus on active motion, bony tenderness, or absence of palpable warmth of synovium), age between the 50 and 75 years old, Body Mass Index (BMI) between 20 and 30 kg/m2, maximal a score of 7 on the numeric rate scale (NRS) for pain intensity during the past two weeks.

The database of the AMS-OA cohort (Reade) will be screened to identify suitable patients based on the Kellgren-Lawrence (KL) score. This will allow patients with predominantly medial sided osteoarthritis to be identified.

There are several additional inclusion criteria for study B. These include patient satisfaction with the applied gait modification (assessed using the questionnaires in Sections F and G in F1 KneeMo Feedback Questionnaires). In addition, patients should be willing further learn the modifications in training sessions. Finally we require patients to show a clear reduction in the KAM value. Where possible the reduction in KAM (relative to baseline) should be 10%, but this will be at the discretion of the clinicians involved in the decision making process. The

10% KAM reduction is proposed based on previous literature that suggests that this value is attainable through gait retraining and is also clinically relevant in unloading the medial knee joint compartment Shull et al. (2013) and Hunt and Takacs (2014),. Importantly the reduction in knee adduction moment must occur without negative side effects such as a large increase in knee flexion moment or in pain. Furthermore, patients will be included only when there is no clear asymmetry in the change in KAM.

Finally, it is important that patients included in the study are able to walk for 30 minutes independently of a walking frame, crutches or other assistive device (excluding soft braces and orthotics).

4.3 Exclusion criteria

Total knee replacement, rheumatoid arthritis or any other form of inflammatory arthritis (i.e., crystal arthropathy or septic arthritis) are exclusion criteria. Similarly patients with hip osteoarthritis will be excluded. Patients who are already included in any other experimental research study (including but not limited to the Vitamin D study and the COOA study) will also be excluded. Subjects with poor eye sight, which would restrict their ability to understand and use the real time feedback will also be excluded,

4.4 Sample size calculation

The study is powered on the outcome variable external knee adduction moment (KAM).

Study A: Based on a significance level alpha = 0.05, power $(1-\beta) = 0.80$ and an effect size of >0.9 based on the reported changes in Van den Noort et al. [13] (see below for calculation of the effect size), the minimum number of subjects required for a statistically significant difference is 5. However, based on the work of Shull et al. (2013) and Hunt and Takacs (2014), we anticipate a smaller effect size when the intervention is used in patients with knee osteoarthritis than was shown in the initial pilot study with healthy controls. Moderate effect sizes (based on the KAM) were calculated from the data in the afore mentioned studies. Based on an anticipated small effect size of 0.45, significance level of 0.05 and power (1- β)=0.80, the minimum number of subjects required is 41. This is calculated using a two tailed t-test, assessing the difference between two dependent means (i.e. the differences in the KAM with and without feedback) [76;77].

Effect size calculations

calculated using $d = \frac{u_1 - u_2}{\sigma}$ where σ is the pooled standard deviation.

Version number: 5, 18-05-16

Van den Noort et al. (2015) [13]

| | Mean (Standard | Where found |
|--|-------------------------|---------------|
| | deviation) ^a | |
| KAM during early stance without feedback | 2.17 (1.03) | Table 2, page |
| (baseline): | | 280 |
| KAM during early stance with feedback ^b | 1.08 (1.07) | Table 2, page |
| | | 280 |

^aStandard deviation calculated from the standard error reported in the table (i.e standard error multiplied by square root of the number of subjects).

^bEffect of different types of feedback not statistically significant; therefore the data presented here is the mean of the five different feedback types used in the study.

Shull et al. (2013) [41]

| | Mean (Standard deviation) ^a | Where found | | |
|--------------------------------|--|--------------------|--|--|
| KAM (first peak) at baseline: | 3.11 (1.40) | Table 2, page 1023 | | |
| KAM (first peak) post training | 2.61 (1.47) | Table 2, page 1023 | | |

Hunt and Takacs 2014 [3]

| | Mean (Standard deviation) ^a | Where found | | |
|--------------------------------|--|-------------------|--|--|
| KAM (second peak) at | 2.87 (0.92) | Table 2, page 909 | | |
| baseline: | | | | |
| KAM (second peak) at follow up | 2.57 (0.84) | Table 2, page 909 | | |

Study B: Based on a significance level alpha = 0.05, power $(1-\beta) = 0.80$, and an anticipated effect size of 0.45 (as above) we require a minimum of 79 participants per group for a between group comparison (i.e. comparison of control and intervention group). This is calculated using a two tailed t-test, assessing the difference between two independent means. Since this is an initial feasibility study, it may not be feasible to recruit such a large number of subjects per group. Therefore we propose that a within group comparison of the baseline to post training may be more suitable. We also anticipate a higher effect size, due to the multiple training sessions. For a within group analysis, using the parameters as specified above and effect size of 0.6, a total of 24 patients are required. This is calculated using a two tailed t-test, assessing the difference between two dependent means (i.e. the differences in the KAM pre and post training) [76;77]. **To account for subject withdrawal we will aim to recruit 30 patients in total.**

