| | knee joint centre to the line of action of the ground reaction force in |
| | the frontal plane This in turn has the effect of reducing the moment. |
| 2) Foot | In a study of 14 young healthy subjects, toe in strategy was |
| Progression | successfully used to reduce the KAM, during early stance[13]. Shull |
| Angle – Toe in | et al. (2012) tested the effectiveness of toe-in gait in a group of 12 |
| | subjects with medial KOA and found a significant reduction in the |
| | first peak of the KAM [10]. Similarly in a six week gait re-training |
| | program, Shull et al. (2013) used feedback to encourage increased |
| | toe-in position [41]. After six weeks gait re-training the first peak |
| | KAM was reduced by 20%. Wheeler et al. (2011) healthy subjects |
| | with feedback on KAM and gave suggestions based on previous |
| | studies of how to reduce the KAM. They found that most subjects, |
| | 14/16, opted for a toe-in gait modification [7]. |
| | |
| | Increasing the internal rotation of the foot (toe in) has the effect of |
| | shifting the knee joint centre (KJC) medially and hence closer to the |
| | CoP. This in turn has the effect of reducing the moment arm from the |
| | KJC to the line of action of the force, as with an increase in step |
| | width, which reduces the KAM. It has also been suggested that the |
| | biomechanical reasoning for the reduction in the moment arm is a |
| | shift in the centre of pressure laterally due to an externally rotated |
| | heel [10] This is in agreement with the finding that the KAM is |
| | typically only reduced in the first peak and not throughout stance. |

| 3) Foot | Hunt and Takacs (2014) trained 15 subjects with medial knee OA to |
|----------------|--|
| Progression | walk with a toe-out gait [3] over a ten week gait modification |
| Angle – Toe | program. At the end of the of the program, second stance KAM was |
| out | significantly reduced. Patients also benefited from a reduction in pain |
| | and an improvement in function as indicated by changes in the |
| | Western Ontario and McMaster Universities Osteoarthritis Index |
| | (WOMAC) score. Van den Noort et al. (2013) also reported a |
| | decrease in second peak KAM with an increased toe out position, in |
| | their study of 14 young healthy subjects [13]. However, in this |
| | investigation, the peak KAM in early stance was increased beyond |
| | the normal range. Although first peak KAM was not significantly |

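### The effect sizes behind the 80% power (0.45 in Study A, 0.6 in Study B) do not follow from the protocol's own formula and data, so the stated power is unsupported

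*Protocol*

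**What the plan says.** Protocol section 4.4 powers the trial on the knee adduction moment (KAM). It defines effect size as the difference of two means divided by their pooled SD. It tabulates means and SDs from one healthy-subject feedback study and two knee osteoarthritis retraining studies, and says effect sizes were calculated from the latter two.

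- **Healthy-subject study:** for an effect size above 0.9, "the minimum number of subjects required for a statistically significant difference is 5".
- **Study A:** "Based on an anticipated small effect size of 0.45, significance level of 0.05 and power" of 0.80, "the minimum number of subjects required is 41", by a two-sided t-test for dependent means.
- **Study B, two-group option (set aside as perhaps not feasible):** "anticipated effect size of 0.45 (as above) we require a minimum of 79 participants per group".
- **Study B, as planned:** "We also anticipate a higher effect size, due to the multiple training sessions". The effect size becomes 0.6, which gives 24 patients by the same paired test. Thirty are recruited to allow for withdrawal.

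Table 1 in section 1 describes the two osteoarthritis studies. The first is introduced with "Similarly in a six week gait re-training". In the second, patients were trained to "walk with a toe-out gait [3] over a ten week gait modification".

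**The concern.** The section prints a formula, the data and a test, and then uses effect sizes that the three do not produce. Both osteoarthritis values come out below 0.45, although the text calls the calculated values moderate and 0.45 small. The formula also standardises by the spread between patients, whereas the named test depends on the spread of within-patient change. Study B's increase to 0.6 rests only on repeated sessions, a feature the source studies share.

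At stake is what 41, 24 and 30 patients can detect on the main endpoint. If the within-patient correlation is modest, a Study B result short of significance would say much less than 80% power implies.

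**Working it through.** **Inputs (all from section 4.4).** Two-sided alpha 0.05, power 0.80. KAM mean (SD):
- six-week study: 3.11 (1.40) to 2.61 (1.47)
- ten-week study: 2.87 (0.92) to 2.57 (0.84)
- healthy subjects: 2.17 (1.03) to 1.08 (1.07)

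**Method.** Paired t-test power from the noncentral t distribution with n − 1 degrees of freedom and noncentrality dz·√n, where dz is the mean change divided by the SD of within-patient differences.

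**Step 1: the plan's patient numbers.** dz = 0.45 gives n = 41 (power 80.3%). dz = 0.6 gives n = 24 (power 80.4%). Independent groups at d = 0.45 give 79 per group. All three reproduce.

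**Step 2: the plan's formula on the plan's data.** d = (mean1 − mean2) / √((s1² + s2²)/2).
- six-week: 0.50 / 1.435 = 0.348
- ten-week: 0.30 / 0.881 = 0.341
- healthy: 1.09 / 1.050 = 1.04

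Neither osteoarthritis value reaches 0.45 or 0.6.

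**Step 3: conversion for a paired test.** dz = (mean1 − mean2) / √(s1² + s2² − 2·r·s1·s2). This agrees with d only near r = 0.5. The protocol gives no r, so r is an assumption here and a range is shown. The two figures in each range come from the two osteoarthritis studies.

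| r assumed | dz | n for 80% | Power, 41 | Power, 24 | Power, 30 |
|---|---|---|---|---|---|
| 0.5 (d as printed) | 0.34-0.35 | 67-70 | 57-59% | 36-37% | 44-45% |
| 0.7 | 0.44-0.45 | 41-43 | 78-80% | 54-56% | 64-66% |
| 0.8 | 0.53-0.55 | 28-30 | 92-93% | 71-73% | 81-83% |

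Solving for r: dz = 0.45 needs r = 0.70 (six-week) or 0.72 (ten-week). dz = 0.6 needs r = 0.83 or 0.84.

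**Step 4: Study B without the increase.** At 0.45, power is 56% with 24 patients and 66% with 30.

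**Step 5: the figure of 5.** An effect size of 0.9 needs 12 patients and 1.04 needs 10. With 5 patients, power is 34% and 43%. Five patients suffice only at dz of about 1.7, which the healthy-subject data reach at r of about 0.82.

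**Step 6: the 79 per group.** It follows from 0.45. With the printed d of 0.348 and 0.341 it would be 131 and 137 per group.

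**The case against.** The strongest reply is that a correlation was used and not reported. At r = 0.82 the healthy data give dz = 1.73 and the stated 5 patients. The osteoarthritis data then give 0.56-0.58, which could be called moderate, and 0.45 becomes a cautious step down. This is coherent, but no such r appears in the protocol and the printed formula has no place for one. Even at that r, 24 patients give 75-78% power. What stands is that the fault may be an omitted conversion rather than inflated effect sizes.

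Other points stand in part:
- 0.45 is described as anticipated, and it lies between the osteoarthritis values and the healthy-subject 1.04. Study A also tests direct KAM feedback, unlike the toe-in and toe-out programmes. But the text offers no working from the data to 0.45.
- Table 1 quotes a 20% first-peak reduction for the six-week study, against 16% from the tabulated means (0.50 / 3.11). Using 20% gives d = 0.43 and n = 44: closer to 0.45, still not it, and well short of 0.6.
- The 0.6 can be read as a judgement relative to Study A's single session, so to say that the training effect is counted twice would be too strong. Section 4.2 also admits to Study B only patients with a clear KAM reduction, which could raise the effect. Section 4.4 does not use that argument.

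A reader might infer that 0.45 cannot serve both the paired and the independent test, or that 79 is an error. Neither follows: the two effect sizes coincide at r = 0.5, and 79 is correct for 0.45.

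**Conclusion.** The inconsistency is established from section 4.4 alone: the printed formula and data give 0.35 and 0.34, not 0.45 or 0.6. The standardiser is not the one the named test needs, and the reason for 0.6 does not distinguish Study B from its sources. The 5 does not follow from the effect size stated for it.

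A reader might go further and conclude that neither study has 80% power. The documents do not show that. With r of about 0.70-0.72, 41 patients give about 80%; with r of about 0.83-0.84, 24 patients do. The low figures of 57-59% and 36-37% hold if the printed d is entered directly, which amounts to r of about 0.5. The 80% is unsupported and depends on an unstated r. Study B is the more exposed, since it needs the higher correlation.

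Nor does the protocol say that a null Study B result would count against the intervention; it presents Study B as proof of concept. These figures assume that the source means and SDs are as tabulated and carry over to this population.

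**What to change.** Keep the patient numbers and rewrite section 4.4:

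1. Print the computed values, 0.35 and 0.34, and settle whether they are called small or moderate.
2. State an assumed r, or an SD of within-patient differences, with its basis, and convert to a paired effect size.
3. Restate power for 41, 24 and 30 patients over r = 0.5 to 0.8.
4. Replace the repeated-sessions reason for 0.6 with one the sources do not already contain, such as the responder selection in section 4.2, or drop 0.6.
5. Correct or delete the 5.
6. Note that 79 per group follows from 0.45 and would be 131-137 with the printed values.

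Study A's SD of differences should not be carried into Study B unadjusted. It comes from a single session, while Study B compares measurements six weeks apart, which may correlate less.

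The cost is a rewording. No patients or procedures are added, but the stated power becomes less favourable or explicitly conditional on r.

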5. METHODS

5.1 Study parameters/endpoints

5.1.1 Main study parameter/endpoint

The main study parameter will be the **external knee adduction moment (KAM).** The KAM is determined by the ground reaction force (GRF) and its lever arm in the frontal plane and considered a surrogate for medial compartment loading.

The two KAM peaks (in early and late stance) have been linked to the presence, severity, and progression of knee OA [10;15]. Gait modification (e.g. toe-out/in, trunk sway, step width, medial thrust, hip rotation etc.) have been shown to influence the KAM (peaks in early and late stance, KAM during mid-stance and KAM impulse (area under curve) [12;13;43].

For study B, the change in KAM over the 6 weeks training period and at 3 and 6 month follow-ups will be evaluated.

5.1.2 Secondary study parameters/endpoints (if applicable)

The first secondary parameter is the external knee flexion moment (KFM, determined by the GRF and its lever arm in the sagittal plane). The KFM has been shown to play an important role in medial compartment loading and has an interaction with the KAM and internal knee load [13;18;40;78;79]. Pain can cause patients to stiffen the knee during gait, which has a direct influence on the KFM since this alters the lever arm.

Pain is also a secondary study parameter (as measured with the NRS scale), particularly in study B, where it will be assessed on a weekly basis (i.e. at each training session). Patient reported outcome measures are becoming increasingly important in experimental studies such as the proposed study. Therefore, the WOMAC questionnaire will be used to assess changes in pain, function and stiffness of the knee. Patients will be asked to complete this questionnaire five times 1) during Study A and then where applicable to the individual patient 2 and 3) at the start and end of the training phase in Study B 4) at the three month follow up and 5) at the six month follow up.

The amount of muscle co-contraction is also a secondary study parameter, measured with electromyography (EMG) (medial muscles: vastus medialis, medial hamstrings, medial

gastrocnemius; lateral muscles: vastus lateralis, lateral hamstrings, lateral gastrocnemius; and the rectus femoris). Co-contraction will influence the load on the knee [21;27;80-82].

Finally, the kinematic strategies (i.e. joint angles and temporal-spatial parameters like gait velocity, step width and step length) that patients use to decrease the KAM are secondary study parameters.

